Change from Baseline in number of days over a week with sleep interrupted due to UC symptoms at Week 16 as assessed by the UC symptom daily diary.
- Change from Baseline at Week 8 in Inflammatory Bowel Disease Questionnaire (IBDQ) total score.
Change from Baseline at Week 16 in IBDQ total score.

- Achievement of no abdominal pain at Week 8 as assessed by the UC symptom daily diary.
Achievement of no abdominal pain at Week 16 as assessed by the UC symptom daily diary.
- Achievement of no bowel urgency at Week 8 as assessed by the UC symptom daily diary.
Achievement of no bowel urgency at Week 16 as assessed by the UC symptom daily diary.
- Change from Baseline at Week 8 in Functional Assessment of Chronic Illness (FACIT)-Fatigue.
Change from Baseline at Week 16 in FACIT-Fatigue.

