8.0 Handling of Potential Intercurrent Events for the Primary and Secondary Endpoints

The primary and secondary efficacy endpoints (defined in Section 3.1 and Section 3.2) will be analyzed based on the ITT Population and the following methods will be used to address potential intercurrent events.

Intercurrent events (ICE):

ICE1: Premature discontinuation of study treatment

A treatment policy strategy will be used to handle ICE1, namely, available data collected will be used regardless of premature discontinuation of study treatment.

ICE2: Initiation or dose escalation of UC-related corticosteroid (defined as below) or initiation of any TIM therapy (including biologics and non-biologics) for UC. A composite strategy will be used to handle ICE2, namely, subjects will be considered as not achieving response at or after ICE2.

UC-related corticosteroid ICE is defined as:

- Subjects who were not on UC-related corticosteroids (systemic or locally acting corticosteroids for UC) at Baseline initiate UC-related corticosteroids during the study.
- Subjects who were on UC-related systemic corticosteroids at Baseline who have dosage increased to greater than the prednisone equivalent dose of corticosteroid taken at Baseline, or initiation of any rectal corticosteroids during the study regardless of rectal corticosteroid dose.

The time of ICE2 is defined as the date when either of the two scenarios above first occurs for a subject. As such, the subject will be considered as a "non-responder" for the efficacy endpoint on or after the date of ICE2 through the end of the study. In the scenario when both ICE1 and ICE2 occur, data will be used on or after the date of ICE1 until ICE2, which the subject will be considered as a "non-responder" for the efficacy endpoint on or after the date of ICE2.

Same intercurrent events handling approaches will be used for additional efficacy endpoints, except for:

- For continuous endpoints, data collected on or after ICE2 will be excluded from the analysis (i.e., treated as missing data) handled by mixed effect model repeat measurement (MMRM).
- For time-to-event endpoint, subjects will be censored at ICE2.

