9.0 Efficacy Analyses

9.1 General Considerations

All efficacy analyses will be conducted on the ITT Population.

The Primary Analysis will be performed after all subjects have completed the Week 8 assessment or withdrawn from the study.

The final analysis will be performed after all subjects have either withdrawn from the study or completed the Week 16 assessment, and completed safety follow-up.

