9.2.2 Continuous Endpoints

MMRM will be the primary approach for the analysis of continuous variables with more than one post Baseline assessment. MMRM analysis will be conducted using mixed-effect model including observed measurements at all visits. For the MMRM analysis, data collected on or after the date of ICE2 will be excluded. The mixed model includes the categorical fixed effects of visit, Baseline corticosteroid use (yes vs no), Baseline Mayo endoscopic sub-score (2 vs 3), prior TIM therapy failure (Yes vs No) and the continuous fixed covariate of Baseline measurement, if applicable. An unstructured variance covariance matrix will be used. If there is a convergence issue, an autoregressive (1) or compound symmetric (CS) covariance structure matrix will be used. The parameter estimations are based on the assumptions of data being missing at random and using the method of restricted maximum likelihood (REML).

Additional approaches, such as Return-to-Baseline Multiple Imputation (RTB-MI), in which data collected on or after the date of ICE2 will be imputed by Baseline values generated from MI model may be conducted for selected continuous endpoints.

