9.5 Additional Efficacy Endpoints and Analyses

Additional efficacy endpoints described in Section 3.3 will be summarized at scheduled timepoints.

For additional binary endpoints, point estimate and 95% CI using normal approximation will be provided for the response rate of the ABBV-668 group. For additional continuous endpoints, the LS-mean and 95% CI will be reported for the ABBV-668 group using MMRM model, which includes visit, Baseline corticosteroid use (yes vs. no), Baseline

Mayo endoscopic sub-score (2 vs 3), TIM (including biologic and non-biologic) failure (Yes vs No) and Baseline measurement, if applicable. For endpoints with a single post-baseline visit, analysis of covariance (ANCOVA) will be used. Same covariates except for visit will be used. Similar analysis using RTB-MI may be performed as sensitivity analysis.

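### IBDQ and FACIT-Fatigue are first measured after treatment at Week 8, so subjects rescued or out of the study before then drop out of the mean change, which is likely overstated

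*SAP*

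**What the plan says.** SAP 8.0 defines the rescue event as "ICE2: Initiation or dose escalation of UC-related corticosteroid (defined as below) or initiation of any TIM therapy (including biologics and non-biologics) for UC". For binary endpoints the subject is a non-responder from that date. Continuous endpoints are an exception: "For continuous endpoints, data collected on or after ICE2 will be excluded from the analysis (i.e., treated as missing data". SAP 9.2.2 repeats this: "For the MMRM analysis, data collected on or after the date of ICE2 will be excluded". The model there is an MMRM under missing at random, with Baseline as a covariate. SAP 9.5 substitutes ANCOVA where there is only one post-baseline visit.

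Stopping study drug is handled differently: "available data collected will be used regardless of premature discontinuation of study treatment". Protocol 5.6 keeps such subjects in scheduled follow-up unless they withdraw consent.

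SAP 3.3 lists among the additional endpoints "Change from Baseline at Week 8 in Inflammatory Bowel Disease Questionnaire (IBDQ) total score", with a Week 16 counterpart and the same pair for FACIT-Fatigue. Protocol Appendix D and Operations Manual 2.1 schedule both questionnaires at Baseline, Week 8 and Week 16 only. Operations Manual 3.4 limits tablet entry to the scheduled visits, so an early or unscheduled entry is not possible.

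Return-to-Baseline multiple imputation appears twice, both times as an option. SAP 9.2.2 says that values on or after rescue, imputed by Baseline values, "generated from MI model may be conducted for selected continuous endpoints". SAP 9.5 says: "Similar analysis using RTB-MI may be performed as sensitivity analysis".

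**The concern.** An MMRM copes with dropout by borrowing from a subject's earlier post-baseline visits. For these two questionnaires there are none before Week 8. With Baseline on the right-hand side of the model, a subject without a usable post-baseline value is not in the likelihood at all. The Week 8 LS-mean then describes subjects who were neither rescued nor lost before Week 8.

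If rescue and withdrawal follow poor response, that group did better than the treated population. In a randomised trial some of this selection might be shared between arms. Here the single-arm mean change is the result, so nothing offsets it.

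The SAP is more cautious elsewhere. For binary endpoints, SAP 9.2.1 entertains missing at random only where it is reasonable, such as pandemic or geo-political causes, and otherwise counts missing as failure. For continuous endpoints the assumption covers every cause, rescue included.

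**Working it through.** The plan states no figure for these endpoints. Its one design figure, more than 90% probability of success with 40 subjects (SAP 2.4), concerns the binary primary endpoint and is not touched by this point.

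**Inputs.** From the documents: the exclusion rule and model (SAP 8.0, 9.2.2, 9.5), the visit schedule (Protocol Appendix D, Operations Manual 2.1), and about 40 subjects (SAP 2.4). Assumed: the share r lost before Week 8 (5% to 30%) and, for the simulation only, a true mean IBDQ change of 35 points.

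**Step 1: who contributes to the Week 8 mean.**

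| Subject | IBDQ/FACIT-Fatigue model | Binary endpoints |
|---|---|---|
| Attends Week 8, no rescue | contributes | as observed |
| Off drug, no rescue, still followed | contributes | as observed |
| Rescued before Week 8, still followed | values collected but excluded; contributes nothing | non-responder |
| Left the study before Week 8 | no value, since the PD visit does not collect one | non-responder |

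**Step 2: formula.** Let m be the mean change among contributors (approximately the LS-mean) and d the mean change assigned to lost subjects under a chosen reference. The full-population mean is (1−r)m + r·d, so

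overstatement = m − [(1−r)m + r·d] = r(m − d).

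It is positive if d < m, zero if d = m, and negative if d > m. With d = 0 (no change from Baseline), the relative overstatement is m/[(1−r)m] − 1 = r/(1−r).

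**Step 3: numbers for d = 0.**

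| r | Lost of 40 | r/(1−r) |
|---|---|---|
| 5% | 2 | 2/38 = 5% |
| 10% | 4 | 4/36 = 11% |
| 15% | 6 | 6/34 = 18% |
| 20% | 8 | 8/32 = 25% |
| 30% | 12 | 12/28 = 43% |

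A milder reference takes lost subjects as improving half as much as contributors (d = m/2). The relative overstatement is then (r/2)/(1 − r/2): 0.05/0.95 = 5% at r = 10%, and 0.10/0.90 = 11% at r = 20%.

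**Step 4: simulation.** This used 200,000 subjects, a true Week 8 change of 35 (SD 35), correlation 0.8 between adjacent visits, and loss driven by poor Week 4 and Week 8 change. All of these are assumptions.

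| r | Reported, first measured at Week 8 | Reported if Weeks 2 and 4 existed | No-rescue mean | Return-to-Baseline mean | Treatment policy, 40-point gain after rescue | Treatment policy, 80-point gain |
|---|---|---|---|---|---|---|
| 5% | 38.0 | 36.2 | 35.0 | 36.1 | 37.0 | 39.0 |
| 10% | 40.4 | 37.4 | 35.0 | 36.4 | 39.0 | 43.0 |
| 20% | 44.6 | 39.6 | 35.0 | 35.7 | 43.0 | 51.0 |
| 30% | 48.8 | 42.2 | 35.1 | 34.2 | 47.1 | 59.1 |

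- Reported over return-to-Baseline reproduces Step 3: 40.43/36.39 = 1.11 and 44.62/35.69 = 1.25.
- Against the no-rescue mean, the excess is 40.43/35.02 − 1 = 15% at r = 10%. This is a strong-dependence case: lost subjects would have averaged (35.02 − 0.9 × 40.43)/0.1 = −13.7, a worsening.
- Earlier visits, had they existed, would have cut the excess at 10% from 5.4 to 2.3 points (37.36 − 35.02). So much of the problem comes from the schedule gap.
- When loss was unrelated to response, the reported and no-rescue means agreed to within 0.01 at every r.
- With an assumed 80-point gain after rescue, the reported mean falls below the treatment-policy mean.

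**The case against.** The best defence is that SAP 8.0 openly makes continuous endpoints an exception and SAP 9.2.2 states its missing-data assumption. Return to Baseline is a different target from the one chosen, so r/(1−r) measures the distance between two targets and is not purely an error. That stands. It is why the size is given against a named reference and why the main analysis need not be replaced. The model also adjusts for Baseline corticosteroid use, endoscopic subscore and prior TIM failure, which may absorb part of the selection.

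Some stronger readings are tempting but unsupported:

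- *The improvement is certainly overstated.* The bias against the no-rescue mean is nil if loss is unrelated to response, and the sign can reverse against treatment policy.
- *Every continuous endpoint has the problem.* SFS, RBS, hs-CRP and FCP all have data before Week 8. Incontinence and sleep interruption are reported at Weeks 8 and 16, but they come from a diary completed daily (Operations Manual 3.4), so earlier data exist. These endpoints are less affected.
- *Anyone who stops drug is lost.* They are not: their data are collected and used. Only rescue or leaving the study removes them.
- *The SAP contradicts its ITT rule.* "All efficacy analyses will be conducted on the ITT Population" names the analysis set. A likelihood model with missing outcomes does not contradict it, although the number contributing should be visible.

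It is also fair that these are additional endpoints in a Phase 2a study, with no success rule attached.

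**Conclusion.** The point holds for IBDQ and FACIT-Fatigue. The documents establish the mechanism: subjects rescued or out of the study before Week 8 contribute nothing to the main analysis of either endpoint. The upward direction is likely but not certain. It rests on the assumption that those subjects would have done worse than the rest.

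Against no change from Baseline, with a positive mean improvement, the overstatement is 11% if 4 of 40 subjects are lost and 25% if 8 of 40 are. If lost subjects would have improved half as much as the others, these figures fall to 5% and 11%. The documents give no rescue or withdrawal rate, so the actual size cannot be stated.

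The optional imputation does not settle the matter. It is not committed for either endpoint, and it is described only for data after rescue, not for study withdrawal without rescue. Primary, secondary and other binary endpoints are unaffected. This is an inexpensive improvement to secondary reporting and does not threaten the trial's conclusion.

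**What to change.** In SAP 9.2.2 and 9.5, for IBDQ and FACIT-Fatigue, change RTB-MI from optional to *will be reported beside the main analysis*. Define it to cover:

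- values on or after rescue (ICE2);
- values missing because the subject left the study before Week 8;
- but not values missing for reasons where missing at random is reasonable, such as pandemic or geo-political causes. These stay under ordinary multiple imputation, in line with SAP 9.2.1.

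Report the number of ITT subjects contributing to each Week 8 LS-mean. The MMRM or ANCOVA stays as the main analysis.

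The cost is SAP wording and two extra tables, using a method the SAP already names. The downside for the sponsor is that somewhat smaller mean changes will appear beside the main ones. No visit, assessment or primary or secondary analysis changes.

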9.0 Efficacy Analyses

9.1 General Considerations

All efficacy analyses will be conducted on the ITT Population.

The Primary Analysis will be performed after all subjects have completed the Week 8 assessment or withdrawn from the study.

The final analysis will be performed after all subjects have either withdrawn from the study or completed the Week 16 assessment, and completed safety follow-up.

9.2 Handling of Missing Data

9.2.1 Categorical Endpoints

For binary efficacy endpoints, the primary approach to handle missing data will be non-responder imputation (NRI). The NRI approach categorizes any subject who does not have an evaluation during a pre-specified visit window as a non-responder for the visit.

In cases data missing at random can be reasonably assumed (e.g., missing due to pandemic or geo-political reasons), NRI while incorporating multiple imputation (NRI-MI) may be performed as additional approach.

In addition, AO analysis will be performed. The AO analysis will not impute values for missing observations, and thus a subject who does not have an evaluation on a scheduled

visit will be excluded from the AO analysis for that visit. All observed data will be used in AO analysis.

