4 INVESTIGATIONAL PLAN

4.1 Overall Study Design and Plan

Study M21-446 is a Phase 2a, multicenter, open-label proof of concept study to investigate the efficacy and safety of ABBV-668 in subjects with moderate to severe UC. The study contains a 30-day screening period, 16-week treatment period, and a 30-day follow up period from the last dose of study drug.

Approximately 40 subjects will be enrolled in this study.

[figure not shown]
An endoscopy is required at Screening and at Week 8 to evaluate endoscopic improvement. To explore the time course of ABBV-668 efficacy, subjects will continue through Week 16. An endoscopy will be performed at Week 16 for subjects:

- Who have an endoscopic subscore of ≥ 1 at the Week 8 endoscopy; or
- Who have an endoscopic subscore of 0 at the Week 8 endoscopy AND have subsequent worsening of their disease (as assessed by the investigator) after the Week 8 endoscopy.

The schematic of the study is shown in [Figure 1](#). Details regarding study procedures are provided in the Operations Manual ([Appendix F](#)).

See Section [5.1](#) for information regarding eligibility criteria.

Figure 1. Study Schematic

BID = twice a day

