2.2 Study Design Overview

Study M21-446 is a Phase 2a, multicenter, open-label proof of concept study to investigate the efficacy and safety of ABBV-668 in subjects with moderate to severe UC. The study contains a 30-day screening period, 16-week treatment period, and a 30-day follow up period from the last dose of study drug.

[figure not shown]
Approximately 40 subjects will be enrolled in this study.

An endoscopy is required at Screening, and at Week 8 to evaluate endoscopic improvement. In order to explore the time-course of ABBV-668 efficacy, subjects will continue through Week 16. An endoscopy will be performed at Week 16 for subjects:

- Who have an endoscopic sub-score ≥ 1 at the Week 8 endoscopy; or
- Who have an endoscopic sub-score of 0 at the Week 8 endoscopy AND have subsequent worsening of their disease (as assessed by the Investigator) after the Week 8 endoscopy.

The schematic of the study is shown in Figure 1.

Figure 1. Study Schematic

BID = twice a day

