3.0 Endpoints

Definitions of Efficacy Endpoints

Clinical Remission per Adapted Mayo Score: stool frequency subscore (SFS) ≤ 1 , and not greater than Baseline, rectal bleeding subscore (RBS) = 0, and endoscopic subscore (ESS) ≤ 1

Clinical Response per Adapted Mayo Score: decrease from Baseline ≥ 2 points and $\geq 30\%$, PLUS a decrease in RBS ≥ 1 or an absolute RBS ≤ 1

Clinical Response per Partial Adapted Mayo Score: decrease from Baseline ≥ 1 points and $\geq 30\%$, PLUS a decrease in RBS ≥ 1 or an absolute RBS ≤ 1

Clinical Remission per Full Mayo Score: Full Mayo score ≤ 2 with no subscore > 1

Clinical Response per Full Mayo Score: decrease from Baseline ≥ 3 points and $\geq 30\%$, PLUS a decrease in RBS ≥ 1 or an absolute RBS ≤ 1

Endoscopic Improvement: Mayo endoscopic subscore (ESS) of 0 or 1. Note that evidence of friability during endoscopy in subjects with a Mayo ESS of 0 or 1 will confer an endoscopic subscore of 2.

Endoscopic Remission: Mayo ESS = 0

Histologic remission: Geboes score of < 2.0

Histologic-endoscopic mucosal improvement: Mayo ESS ≤ 1 and Geboes score ≤ 3.1

Mucosal Healing: endoscopic (Mayo ESS = 0) and histologic remission (Geboes score of < 2.0).

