3.3 Additional Efficacy Endpoints

In addition, the primary and secondary efficacy endpoints will be analyzed at all other scheduled visits during which the assessments are measured. The following endpoints will also be evaluated at scheduled visits during which the assessments are measured, unless otherwise specified:

- Achievement of clinical response per Full Mayo score over time in subjects with a Full Mayo score of 6 to 12 at Baseline.
- Achievement of clinical remission per Full Mayo score over time in subjects with a Full Mayo score of 6 to 12 at Baseline (at visits with endoscopy).
- Achievement of SFS = 0, RBS = 0, and ESS = 0 over time (at visits with endoscopy).
- Achievement of SFS = 0, RBS = 0, and ESS \leq 1 over time (at visits with endoscopy).
- Time to clinical response per Partial Adapted Mayo.
- Achievement of SFS \leq 1 over time.
- Achievement of RBS = 0 over time.
- Change from Baseline in RBS over time.

- Change from Baseline in SFS over time
- Achievement of histologic-endoscopic mucosal improvement over time (at visits with endoscopy).
- Achievement of histologic remission over time (at visits with endoscopy).
- Achievement of mucosal healing (endoscopic and histologic remission) over time (at visits with endoscopy).
- Change from Baseline in number of extraintestinal manifestations (EIM) over time (as captured in the EIM electronic case report form [eCRF]).
- Change from Baseline in fecal calprotectin (FCP) over time.
- Achievement of FCP below 150 mg/kg over time.
- Achievement of FCP below 250 mg/kg over time.
- Change from Baseline in high sensitivity C-reactive protein (hs-CRP) over time.
- Achievement of no nocturnal bowel movements at Week 8 as assessed by the UC symptom daily diary.
Achievement of no nocturnal bowel movements at Week 16 as assessed by the UC symptom daily diary.
- Achievement of no tenesmus at Week 8 as assessed by the UC symptom daily diary.
Achievement of no tenesmus at Week 16 as assessed by the UC symptom daily diary.
- Change from Baseline in number of fecal incontinence episodes per week at Week 8 as assessed by the UC symptom daily diary.
Change from Baseline in number of fecal incontinence episodes per week at Week 16 as assessed by the UC symptom daily diary.
- Change from Baseline in number of days over a week with sleep interrupted due to UC symptoms at Week 8 as assessed by the UC symptom daily diary.

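### Week 16 rule for absent endoscopies scores unscoped sustained endoscopic remitters as non-responders (minor; additional Week 16 endpoints only)

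*SAP*

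**What the plan says.** **Who is scoped at Week 16.** Protocol 4.1 and SAP 2.2 call for a Week 16 endoscopy in two groups: subjects with a Week 8 ESS of 1 or more, and those "Who have an endoscopic subscore of 0 at the Week 8 endoscopy AND have subsequent worsening of their disease" (the SAP: "Who have an endoscopic sub-score of 0 at the Week 8 endoscopy AND have subsequent worsening of their disease"). A Week 8 ESS 0 subject without worsening is in neither group and is called exempt below.

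**What is analysed at Week 16.** SAP 3.3 states that "the primary and secondary efficacy endpoints will be analyzed at all other scheduled visits during which the assessments are measured", and adds histologic, Full Mayo and SFS/RBS/ESS endpoints over time. SAP 9.1 sets the population: "All efficacy analyses will be conducted on the ITT Population".

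**How an absent evaluation is treated.** SAP 9.2.1 makes NRI primary: "The NRI approach categorizes any subject who does not have an evaluation during a pre-specified visit window as a non-responder for the visit". For the as-observed (AO) analysis, "The AO analysis will not impute values for missing observations", and a subject without an evaluation is left out at that visit. Where missing at random is reasonable, "NRI while incorporating multiple imputation (NRI-MI) may be performed as additional approach"; the examples are pandemic and geo-political causes. Protocol 7.4 instead makes NRI-MI the primary approach for the primary and secondary endpoints.

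**Related text.** SAP 9.6 adds an AO summary of three histology-based endpoints, limited to subjects who had the Week 16 endoscopy. Operations Manual 2.1 (Week 16) and 3.16 list that endoscopy without the Week 8 condition.

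**The concern.** The exempt subjects have the best Week 8 endoscopic result and have not worsened. A rule written for missing data treats an assessment that the design never asked for as a failure, and AO removes the same subjects from the denominator. Both specified analyses are therefore selective on the outcome.

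Protocol 4.1 gives exploring the time course of efficacy as the reason for continuing to Week 16. Endoscopic remission is hit hardest, because its sustained Week 8 responders are exactly the subjects not scoped. SAP 9.5 reports these endpoints as a rate with a confidence interval, so a fall from Week 8 to Week 16 could be read as loss of effect when it comes from the scoring rule.

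**Working it through.** The documents state no figure for this point, so there is none to reproduce. The check is a reading of the rules, an endpoint count, and arithmetic per exempt subject.

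**1. Endpoints affected (SAP 3.0 to 3.3).** Five rest wholly on endoscopy or biopsy: endoscopic improvement, endoscopic remission, histologic-endoscopic mucosal improvement, histologic remission and mucosal healing. Six combine ESS with diary or physician's global assessment (PGA) components: Adapted Mayo remission and response, Full Mayo remission and response, and the two SFS/RBS/ESS composites. Operations Manual 8.2 has a missing-data rule for the diary subscores only.

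**2. Size per exempt subject.** With N = 40 (SAP 2.4), k exempt subjects still in response and x responders among those scoped:
- rate counting the exempt = (x + k)/40
- NRI = x/40, low by k/40, which is 1/40 = 2.5 points each
- AO = x/(40 − k), low only if exempt subjects respond more often than scoped ones

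**3. How many are exempt.** Not stated. The one anchor is pooled placebo endoscopic remission in SAP Table D-1: (2 + 2 + 2 + 3)/(122 + 112 + 154 + 174) = 9/562 = 1.6%. That gives 40 × 0.016 = 0.64 subjects, and a probability of 1 − (1 − 0.016)^40 = 0.48 that at least one of 40 has ESS 0. A larger k is an assumption.

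**4. Illustrations (k, the 15/40 rate and full maintenance are assumed).**
- Endoscopic remission, k = 2, no new remission: 2/40 = 5.0%, against NRI 0/40 and AO 0/38.
- Endoscopic improvement, 15/40 = 37.5% maintained:

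| k | NRI = (15 − k)/40 | AO = (15 − k)/(40 − k) |
|---|---|---|
| 1 | 35.0% | 35.9% |
| 2 | 32.5% | 34.2% |
| 4 | 27.5% | 30.6% |

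For scale, the 95% half-width at 15/40 is 1.96 × √(0.375 × 0.625/40) = 15.0 points.

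**5. When is a composite settled without ESS?** Take integer baseline profiles with Adapted Mayo 5 to 9 and ESS 2 or 3. ESS 2 needs SFS + RBS ≥ 3 (10 pairs) and ESS 3 needs ≥ 2 (13 pairs), so there are 23. Consider Week 16 SFS 0 or 1 with RBS 0, the plausible range for subjects doing well: 23 × 2 = 46 profiles.
- *Adapted Mayo response* at the worst ESS of 3. With SFS 0 the total is 3, and all 23 meet a fall of at least 2 points and 30%. With SFS 1 the total is 4, and baseline must be at least 6, which excludes the 7 profiles with baseline 5. Settled: 23 + 16 = 39 of 46.
- *Adapted Mayo remission* is settled only as not met, when SFS 1 exceeds a baseline SFS of 0. Three profiles have baseline SFS 0, so 3 of 46.

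These are counts of profiles, not probabilities. Operations Manual 8.2 averages subscores over 7 days, so real values need not be integers.

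**6. Does multiple imputation help?** By design no non-worsening Week 8 ESS 0 subject has a Week 16 ESS. An imputation model would have to extrapolate from subjects with ESS ≥ 1 or with worsening, under the protocol's rule or the SAP's.

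**The case against.** **An endoscopy never required is not missing data.** SAP 9.2.1 sits under missing data, and SAP 3.3 confines analysis to visits where assessments are measured, for several endpoints to visits with endoscopy. This is arguable. However, 9.2.1 is worded for any subject without an evaluation, 9.1 puts all efficacy analyses on the ITT Population, and 9.6 calls its scoped-only summary additional. That summary shows that conditional scoping was foreseen, but it covers three endpoints and keeps the same selection.

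**The number exempt may be nil.** This stands. The anchor gives a 52% chance that nobody is exempt, although it is a placebo rate that an active drug could exceed. If sites followed Operations Manual 2.1 and 3.16, no subject is exempt.

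**Nothing decisive depends on Week 16.** This also stands. The affected endpoints are additional and carry no decision rule, in a proof-of-concept study without multiplicity control.

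**A table by Week 8 ESS (0 versus ≥ 1) would be enough.** It would not. By design its ESS 0 row would be empty or hold only subjects who worsened, and the fewer-than-10 rule in SAP 9.6 might suppress it.

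**Conclusion.** The point holds as a minor one. Followed literally, SAP 9.2.1 reports a sustained but unscoped Week 8 remitter as a Week 16 failure. NRI endoscopic remission and improvement are then low by 2.5 points per exempt subject still in response. For the three histology-based endpoints the effect per subject is less certain, because ESS 0 does not establish "Histologic remission: Geboes score of < 2.0". For the six composites NRI is the likely reading, but not a stated one.

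A reader might infer three stronger things that the documents do not support:
- *That the efficacy conclusion is at risk.* All subjects are due a Week 8 endoscopy, so the Week 8 primary and secondary results and the sample size are untouched.
- *That the bias is large.* A 10-point shift needs 4 exempt subjects, all still in response. Both are assumptions.
- *That the composites can mostly be resolved without ESS.* Over all 368 integer combinations (23 × 16 Week 16 SFS/RBS pairs), Adapted Mayo remission is settled in 325, always as not met. In the relevant subset it is settled in 3 of 46.

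**What to change.** 1. Reconcile Operations Manual 2.1 (Week 16) and 3.16 with Protocol 4.1 and SAP 2.2. The number exempt depends on which text sites followed.
2. In SAP 9.2.1, flag a Week 16 endoscopy not required by design separately from missing data. Use any Week 16 endoscopy actually done as observed, and state the exempt count beside each affected Week 16 rate.
3. For the eight ESS-based endpoints (endoscopic improvement, endoscopic remission, six composites), report plain NRI as the lower bound. As the upper bound for exempt subjects, carry ESS 0 forward and combine it with the observed Week 16 diary subscores, and PGA for Full Mayo. Limit this to subjects still in the study, with no ICE2 and no recorded worsening. Zero is the best possible ESS, hence an upper bound.
4. Score a composite as known when its observed components give the same result at every ESS from 0 to 3. This mainly helps Adapted Mayo response and rarely remission.
5. For the three histology-based endpoints, keep NRI with the exempt count, and give Geboes carry-forward only as a labelled sensitivity analysis. It can err in either direction, since histology may improve or relapse by Week 16.
6. State that NRI-MI, if used, does not cover exempt subjects.

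**Cost.** SAP wording, a derivation flag, a composite rule and extra rows for the bounds and sensitivity analyses; no new data collection. ESS carry-forward assumes no silent endoscopic relapse and can be too high by up to 2.5 points per exempt subject. The flag also relies on how investigator-assessed worsening was recorded, for which the documents give no criterion.
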